10.4.6 Serious Adverse Event Reporting

All SAEs must be entered into the eCRF within 24 hours of first knowledge of the event by study personnel. It is important that the investigator provide their assessment of relationship to study drug at the time of the initial report. Follow-up information must also be reported within 24 hours of first knowledge. Entry of an SAE (or updated SAE information) into the eCRF will trigger an automatic alert to the designated CRO safety team. Timely notification of an event supersedes the requirement to have all information at the time of the initial report.

If the EDC system is **not available**, the investigator must send a completed paper SAE Report Form to the CRO safety team via email or fax as follows, within 24 hours. If no acknowledgement is received within one working day, the report should be re-submitted.

Safety Report Email Address: [contact]

Safety Report [contact] (US) or [name] (international)

The SAE data must be entered into the eCRF as soon as it becomes available.

The following information must be reported on the eCRF SAE report form:

- Protocol number
- Site and/or Investigator number
- Patient number
- Demographic data
- Brief description of the event

- Onset date and time
- Resolution date and time, if the event resolved
- Current status, if event not yet resolved
- Any concomitant treatment and medication
- Investigator's assessment of whether the SAE was related to investigative product or not
- Outcome of the event if available

The CRO safety team will contact the site for clarification of data entered onto the eCRF, or to obtain missing information. In the event of questions regarding SAE reporting, the site may contact Cmed Drug Safety and Pharmacovigilance via email [contact].

Unexpected serious suspected adverse reactions are subject to expedited reporting to FDA. The CRO safety team is responsible for submitting reports of AEs associated with the use of the drug that are both serious and unexpected to the FDA and to investigators participating in ongoing clinical studies with the study medication, according to 21 CFR 312.32 and the applicable guidance documents. All investigators participating in ongoing clinical studies with the study medication are responsible for prompt submission of these reports to their Institutional Review Board (IRB) or Ethics Committee (EC).

10.4.7 Overdose

No information on treatment of overdose of ulixertinib is currently available. In the event of an overdose, within 24 hours of awareness, the overdose should be reported as an AE and the medical monitor should be notified. All overdose cases will be discussed by the sponsor and medical monitor on a case-by-case basis.

10.4.8 Reporting of Pregnancy

Each pregnancy in a patient or partner of a patient on ulixertinib must be reported to the designated CRO safety team within 24 hours of learning of its occurrence, on a Pregnancy Notification Form and via the contact details noted in Section 10.4.6. If a patient becomes pregnant, study drug administration must be discontinued immediately. The pregnancy should be followed up to determine outcome, including spontaneous or voluntary termination, details of the birth, and the presence or absence of any birth defects, congenital abnormalities, or maternal and/or newborn complications. Follow-up and documentation must occur even if the patient withdraws from the study or the study is completed.

Pregnancy per se is not considered an AE unless there is cause to believe that the study drug may have interfered with the effectiveness of a contraceptive medication.

Hospitalization for normal delivery of a healthy newborn should not be considered a SAE. Abnormal pregnancy outcomes (e.g., spontaneous abortion, fetal death, stillbirth, congenital anomalies, ectopic pregnancy) are considered SAEs and must be reported as such.

The avoidance of pregnancy or fathering a child is suggested for 3 months following the discontinuation of ulixertinib therapy. No information is currently available regarding the effects of ulixertinib on fertility, gestation or subsequent child development.

Any pregnancy within 3 months after the last study drug administration should be reported to the study investigator and to the CRO.

11 STATISTICAL CONSIDERATIONS

11.1 STATISTICAL ANALYSIS PLAN

A formal detailed statistical analysis plan (SAP), covering statistical analyses planned for Part A and Part B, will be developed and finalized prior to the main analysis of Part A data. This section is a summary of the planned statistical analyses at the time of protocol development.

A separate analysis plan will be developed specifically for the safety reviews to be conducted by the SMC.

11.2 SAMPLE SIZE DETERMINATION

11.2.1 Part A

Approximately 38 patients will be recruited into each group in Part A.

With 34 patients in a group and assuming the true ORR is 40%, there is approximately 80% power to reject the null hypothesis that the true ORR is $\leq 20\%$ in that group, with a 1-sided alpha of 5%. Assuming a 10% drop out rate, up to 38 patients will be recruited in each group.

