11.5.5.1 Part A

The primary endpoint for Part A is the overall response rate (ORR) within a group. It will be defined as the percentage of patients achieving a BOR of confirmed CR and/or PR as assessed by the investigator. The ORR will be presented with its 95% confidence intervals (CIs).

All response assessments will be presented using swimmer plots and will be listed by patient.

Sensitivity analyses of the primary analysis will include similar analyses using PP analysis set.

Analyses of secondary efficacy endpoints will include Kaplan-Meier estimates and curves, median DoR and respective 95% CIs for analysis of:

- Duration of response (DoR): time from first response to disease progression or death. Patients with no event will be censored at the last available tumor assessment. This analysis will be based on investigator assessment.
- Progression-free survival over 18 months (PFS): time from first day of trial medication to disease progression or death. Patients with no event will be censored at the last available tumor assessment. This analysis will be based on investigator assessment.
- Overall survival over 18 months (OS): time from first day of trial medication to death. Patients with no event will be censored at the last date the patient is known to be alive.

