### 6.4 SAMPLE SIZE JUSTIFICATION

#### *Part A*

Approximately 38 patients will be recruited into each group in Part A.

With 34 patients in a group and assuming the true ORR is 40%, there is approximately 80% power to reject the null hypothesis that the true ORR is  $\leq 20\%$  in that group, with a 1-sided alpha of 5%. Assuming a 10% drop out rate, up to 38 patients will be recruited in each group.

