### 7.2 PLANNING OF ANALYSES

This SAP covers final analysis for Part A and Part B, although the analysis for Part B will be further described once Part A results are available in an updated SAP version. The planned timing of analysis for Part A is 18 months after the last patient enrolled starts treatment. Since Part B depends on Part A results it is not possible to estimate by when Part B analysis will occur. The SAP will be updated after Part A results are available and the Protocol is amended.

Given that the study was early terminated during Part A, an abbreviated CSR focusing on safety will be prepared. Therefore not all Tables, Listings and Figures planned in SAP version 1 will be required. The Shells table of contents will have an additional column to indicate which outputs will be delivered for the final analysis of Part A.

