### Evaluable Analysis Set

The Evaluable Analysis Set (EAS) will consist of patients from FAS who had the first efficacy evaluation on Study Day 29 $\pm$ 3. Prior to any analysis, all patients data will be reviewed and additional criteria for exclusion from EAS may be added (e.g. occurrence of one or more important protocol deviations). Those cases, if any, will be properly documented in the study report.

For Part A the Full Analysis Set and the Safety Full Analysis Set will be the same. Given that the study was early terminated and an abbreviated CSR focusing mostly on safety data will be prepared, EAS and PP will not be used in any analysis.

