**Table 5. Evaluation of Overall Response**

Target lesions	Non-target lesions	New lesions	Overall response
CR	CR (or no non-target lesions)	No	CR
No target lesion a	CR	No	CR
CR	NE b	No	PR
CR	Non-CR/non-PD	No	PR
PR	Non-PD and NE (or no non-target lesions) b	No	PR
SD	Non-PD and NE (or no non-target lesions) b	No	SD
Not all evaluated	Non-PD	No	NE
No target lesion a	Not all evaluated	No	NE
No target lesion a	Non-CR/non-PD	No	Non-CR/non-PD
PD	Any	Yes or No	PD
Any	PD	Yes or No	PD
Any	Any	Yes	PD
No target lesion a	Unequivocal PD	Yes or No	PD
No target lesion a	Any	Yes	PD

CR = complete response, PR = partial response, SD = stable disease, PD = progressive disease, and NE = not evaluable.

aDefined as no target lesion at baseline.

bNot evaluable is defined as when either no or only a subset of lesion measurements is made at an assessment.

The ORR is defined as the percentage of patients having a confirmed response of either CR or PR. ORR will be calculated with the 95% confidence intervals (CIs). The 95% CIs will be estimated using the Clopper-Pearson method.

For Part B, ORR will be compared between ulixertinib and physician's choice of treatment using a Chi square test or Fisher's exact test as applicable.

Complete and partial response must be confirmed by a repeat assessment performed at > or = 4 weeks after the criteria for response are first met. Date of confirmed CR/PR will be the date of the first CR/PR that qualifies for confirmation. Additionally, patients with no post-baseline efficacy measurement due to reasons accountable for disease progression, will be assessed as non-evaluable and will count in the denominator of the ORR.

BOR will be assessed based on the tumor response at different evaluation time points from baseline until the first documented disease progression for RECIST or the last response assessment if there is no document disease progression at the time of the analysis. The order used to determine BOR is CR>PR>SD>PD, ignoring visits with missing tumor assessments. For SD to qualify for BOR, the SD assessment should be at least 6 weeks after first ulixertinib dose. BOR

date in this case will be the date of the first SD/PR/CR documented after 6 weeks.

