## 11 Changes to Planned Analyses

No major changes to analyses planned in the protocol are expected.

A new analysis population was defined to further investigate efficacy. Although the SAP will be signed and finalized prior to the first study analysis, this new analysis population is for exploratory purposes only.

Demographic and baseline data was planned in the Protocol to be reported for all analysis populations. However, at least for Part A, this will only be reported on FAS. For Part B, this may

be revised and additional tables may be added for each analysis set.

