## 3 List of Tables, Figures and Listings

Part	TFL Type	TFL Number	Title	Population	Included in Final Analysis
	14.1		Demographic Data		
A & B	Table	14.1-1.1	Patient Disposition	All Patients Set	Y
A & B	Table	14.1-1.2	Number of Patients in the Analysis Sets	All Patients Set	Y
A & B	Table	14.1-1.3	Summary of Important Protocol Deviations	Full Analysis Set	Y
A & B	Table	14.1-2.1	Demographics and Baseline Characteristics	Full Analysis Set	Y
A & B	Table	14.1-2.2	Disease History	Full Analysis Set	Y
A & B	Table	14.1-2.3	Summary of Medical History	Full Analysis Set	Y
A & B	Table	14.1-2.4	Summary of Concomitant Diseases	Full Analysis Set	Y
A & B	Table	14.1-3.1	Prior Radiotherapies	Full Analysis Set	Y
A & B	Table	14.1-3.2	Prior Anti-Cancer Therapies	Full Analysis Set	Y
A & B	Table	14.1-3.3	Prior BRAF/MEK inhibitor therapies	Full Analysis Set	Y
A & B	Table	14.1-3.4	Prior Medications	Full Analysis Set	Y
A & B	Table	14.1-3.5	Concomitant Medications	Full Analysis Set	Y
A & B	Table	14.1-4.1	Treatment Exposure	Full Analysis Set	Y
A & B	Table	14.1-4.2	Dosing Interruptions and Adjustments	Full Analysis Set	Y
	14.2		Efficacy Data		
A & B	Table	14.2-1.1.1	Best Overall Response and Overall Response Rate	Full Analysis Set	Y
A & B	Table	14.2-1.1.2	Best Overall Response and Overall Response Rate	Per Protocol Set	
A & B	Table	14.2-1.1.3	Best Overall Response and Overall Response Rate	Evaluable Analysis Set	
A & B	Table	14.2-1.2.1	Overall, Target and Non-Target Lesion Response	Full Analysis Set	Y
A & B	Table	14.2-1.2.2	Overall, Target and Non-Target Lesion Response	Per Protocol Set	
A & B	Table	14.2-1.2.3	Overall, Target and Non-Target Lesion Response	Evaluable Analysis Set	
A & B	Table	14.2-1.3.1	Incidence of New Lesions	Full Analysis Set	Y
A & B	Table	14.2-1.3.2	Incidence of New Lesions	Per Protocol Set	

A & B	Table	14.2-1.3.3	Incidence of New Lesions	Evaluable Analysis Set	
A & B	Table	14.2-1.4.1	Duration of Response (DOR)	Full Analysis Set	
A & B	Table	14.2-1.4.2	Duration of Response (DOR)	Per Protocol Set	

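### The one-sided 5% test of ORR ≤20% that sizes each Part A group is not carried into the analysis sections, whose only planned inference is a 95% CI at a different level

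*Protocol*

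**What the plan says.** The Part A sample size, identical in Protocol 11.2.1 and SAP 6.4, is built on a hypothesis test in each group. The null is ORR ≤20% and the alternative is 40%: "With 34 patients in a group and assuming the true ORR is 40%, there is approximately 80% power to reject the null hypothesis", "with a 1-sided alpha of 5"%. Allowing for 10% drop-out takes 34 to 38 per group.

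The analysis sections contain estimation only. Protocol 11.5.5.1 says: "The ORR will be presented with its 95% confidence intervals (CIs"). SAP 9.8.1 adds the method: "The 95% CIs will be estimated using the Clopper-Pearson method". Shell Table 14.2-1.1.1 ("Best Overall Response and Overall Response Rate") has rows for counts, percentages and 95% CIs. It has no p-value, no 20% reference and no success criterion. The only ORR test described anywhere is the between-arm comparison in Part B.

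SAP version 2.0 was issued after termination: "Given that the study was early terminated during Part A, an abbreviated CSR focusing on safety will be prepared". It nevertheless keeps the sizing statement in 6.4 and marks the FAS version of the ORR table for delivery. On departures from the protocol, SAP 11 says: "No major changes to analyses planned in the protocol are expected".

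**The concern.** A power statement describes a specific decision rule. Here the rule is stated when n is chosen and is then absent from the analysis of the primary endpoint. A reader of the report will have the 20% null and the 80% power figure from SAP 6.4 and one interval per group from the table, and will naturally compare that interval with 20%. A two-sided 95% Clopper-Pearson lower limit exceeds 20% exactly when the exact one-sided binomial test rejects at 2.5%, not at 5%. A group could therefore satisfy the test that justified its size while its only printed interval includes 20%, and nothing in the analysis sections says how to resolve this.

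**Working it through.** Inputs: null rate 0.20, assumed rate 0.40, one-sided alpha 0.05, n=34 (Protocol 11.2.1, SAP 6.4); 38 recruited, from 34/0.9 = 37.8; 95% Clopper-Pearson CI (SAP 9.8.1). Below, X is the number of responders, binomial(n, p).

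**1. The plan's own figure.** Normal approximation with continuity correction, n=34:
- Mean and SD under the null: 34×0.20 = 6.8 and √(34×0.2×0.8) = 2.332.
- Cut-off: 6.8 + 0.5 + 1.645×2.332 = 11.14.
- Mean and SD at 40%: 13.6 and √(34×0.4×0.6) = 2.857.
- Power: Φ((13.6 − 11.14)/2.857) = Φ(0.862) = 80.6%.

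So approximately 80% is reproduced. Without the correction the same method gives 85.0%.

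**2. The exact one-sided 5% test.** Reject at the smallest c with P(X ≥ c | 0.20) ≤ 0.05; power is P(X ≥ c | 0.40).
- n=34: c=11 gives 0.062 (too large) and c=12 gives 0.027. Power 76.7%.
- n=38: c=12 gives 0.062 (too large) and c=13 gives 0.029. Power 81.4%.

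**3. The planned 95% CI, if read against 20%.** The Clopper-Pearson lower limit for x responders is the 2.5% quantile of Beta(x, n−x+1).

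| Result | Exact one-sided p vs 20% | 95% Clopper-Pearson CI or lower limit | 90% Clopper-Pearson lower limit |
|---|---|---|---|
| 12/34 | 0.027 | 19.7% to 53.5% | 21.8% |
| 13/34 | 0.011 | lower limit 22.2% | 24.3% |
| 13/38 | 0.029 | 19.6% to 51.4% | 21.6% |
| 14/38 | 0.012 | lower limit 21.8% | 23.8% |

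The 95% lower limit passes 20% only from 13/34 or 14/38. P(X ≥ 13 | 34, 0.40) = 64.6% and P(X ≥ 14 | 38, 0.40) = 71.0%. The 90% lower limit (5% quantile of the same Beta) passes 20% from 12/34 and 13/38, which is the exact one-sided 5% rule.

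**4. How often the two disagree.** At a true ORR of 40%, P(X=12 | 34) = 12.1% and P(X=13 | 38) = 10.3% per group. These equal the power differences: 76.7 − 64.6 and 81.4 − 71.0, up to rounding.

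**5. Dependence on group size.** For every n from 5 to 38, the exact cut-offs at 5% and 2.5% differ at 21 sizes and coincide at 13 (5, 6, 8, 9, 11, 12, 15, 18, 19, 22, 26, 33, 37).

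**6. Dependence on CI method.** A Wilson 95% interval has lower limits of 21.5% at 12/34 and 21.2% at 13/38. Both exclude 20%, so the disagreement would not arise at these counts.

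**The case against.** The strongest reply is that a sizing test and a conventional 95% interval can coexist. Nobody wrote that success means a lower limit above 20%, so 64.6% and 71.0% are not the power of any planned analysis. This stands. A reader might infer that the primary analysis is underpowered as planned; the documents do not support that, because they define no success rule for the CI. What they do show is that the powered test has no analysis.

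A reader might also infer that the 80% figure is wrong. It is not: step 1 reproduces it, and the text says approximately and names no exact test.

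The numerical disagreement is also specific to Clopper-Pearson, which only the SAP names. On the protocol alone the point is an omission, not a demonstrable conflict in results.

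Finally, the study has stopped, the report focuses on safety, and a test written in now would be specified late in an open-label study. The first two limit the consequence. The third is a fair reason to prefer declaring that no test will be done. However, the null, level and sidedness were already fixed in the sizing section, so only the choice of test statistic is new. Silence leaves that choice open: an uncorrected normal test at n=34 has its cut-off at 6.8 + 1.645×2.332 = 10.64 and would reject at 11/34, where the exact p is 0.062.

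**Conclusion.** The point holds as an inconsistency between sizing and analysis of the primary endpoint. The one-sided 5% test of ORR ≤20% was not carried forward, and the one interval that is planned corresponds, by the SAP's method, to a one-sided 2.5% bound. At the design sizes this affects exactly one responder count per group (12/34 or 13/38). Reading the CI against 20% would cost about 12 points of power at n=34 and 10 points at n=38 relative to the exact one-sided 5% test.

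These figures assume a true ORR of 40%, Clopper-Pearson limits, and a FAS denominator of 34 or 38. The documents do not give the achieved group sizes, so whether any reported group is affected is unknown. With early termination, the consequence is confined to how the reported group ORRs are read against 20%. The correction should be made, but it does not call the sample size or the data into question.

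**What to change.** If the comparison with 20% is to be made, SAP 9.8.1 (and Protocol 11.5.5.1 if the protocol is amended) should say that ORR ≤20% is judged in each group by the exact one-sided 5% binomial test on the FAS. An equivalent statement is a two-sided 90% Clopper-Pearson lower limit above 20%. That means at least 12/34 or 13/38, recomputed for each group's actual size. Label the 95% CI descriptive, add the 90% lower limit to Table 14.2-1.1.1, and note in SAP 6.4 that the exact power of this test is about 77% at n=34 and 81% at n=38.

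If no test will be done because of early termination, say so in SAP 11, and state that the 95% CIs are descriptive and are not a test against 20%.

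The cost is a few sentences and at most one extra table line, with no additional patients. The first option also means stating a slightly less favourable power at n=34.

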11.2.2 Part B

It is not possible to accurately calculate the required sample size until the histologies of interest have been confirmed. Once the histologies of interest have been confirmed these calculations will be repeated and the final sample size confirmed.

Approximately 80-100 patients will be randomized, using a 2:1 ratio, for each histology group in Part B.

Using a 2-sided, log-rank test with a 5% alpha, and assuming a median PFS of 1.7 to 8.5 months (depending on histology) in the physician's choice arm and twice as long on the ulixertinib arm, approximately 80 to 100 patients will be required in each group to achieve 80% power to show a statistically significant difference between the arms. This also assumes that each group will take approximately 24 months to accrue and the analysis is expected to be performed 18 months following the last patient accrued. The anticipated loss to follow-up is estimated to be 10%.

11.3 RANDOMIZATION

Part A of this study is open-label, and all patients enrolled in Part A will be treated with ulixertinib.

Part B of this study is open-label, patients will be randomly assigned to receive either ulixertinib or the physician's choice of treatment in a 2:1 ratio. Also see [Section 8.3](#).

11.4 ANALYSIS SETS

11.4.1 Full Analysis Set

The full analysis set (FAS) will consist of all patients who received at least one dose of study medication. This analysis set will be used for all efficacy analyses.

For Part B, analyses performed on the FAS will allocate patients' treatment group as randomized.

11.4.2 Safety Analysis Set

The safety analysis set will consist of all patients who received at least one dose of study medication. This analysis set will be used for all safety analyses.

For Part B, analyses performed on the safety population will allocate patients' treatment group as actually received.

11.4.3 Per Protocol Analysis Set

The per-protocol (PP) analysis set will consist of all patients of the FAS who completed the study without any major protocol deviations.

11.5 DATA PRESENTATION

Descriptive statistics for continuous variables will include the number of patients, mean, standard deviation, median, minimum, maximum; frequencies and percentages will be displayed for categorical data.

Summary data will be provided separately for Part A and Part B, and by group/tumor histology.

Data will be analyzed using the SAS system software version 9.4 (or later).

11.5.1 Demographic

Demographic characteristics of patients will be summarized in appropriate tables and with descriptive statistics.

The following characteristics will be summarized in the FAS, PP, and safety analysis sets:

- Age
- Gender
- Race
- Ethnicity
- Advanced malignancy information including relapsed or refractory status
- MEK or Atypical BRAF alteration

11.5.2 Baseline Characteristics

Baseline characteristics will be summarized in appropriate tables and with descriptive statistics.

The following characteristics will be summarized in the FAS, PP, and safety analysis sets:

- Body weight
- Height
- ECOG performance status
- Previous cancer therapies

11.5.3 Medical History and Physical Examination

Medical history and physical examination assessments will be summarized in appropriate tables and with descriptive statistics, in the FAS, PP, and safety analysis sets.

